## Insulin Pump Initiation Settings Worksheet

Subject ID:

Test Subject 001

The following information is based on an analysis of the pump settings of more than 100,000 Tandem users and is provided to assist healthcare providers in determining a starting point for pump settings for their patients switching from multiple daily injections to Continuous Subcutaneous Insulin Infusion (CSII).

### Only Input needed for Calculations:

Daily Long Acting Dose of Injection

Insulin:

35

(only basal insulin)  
(Recommend average of 7 days).

Recommended Profile Settings (For single profile with single segment)		
Initial Basal Rate	$= \frac{\text{Long Acting Dose}}{24 \text{ hours}}$	1.46 units/hour (Initial Basal Rate)
Carb Ratio (Insulin to Carb Ratio)	Calculated based on Long Acting Dose	7.1 grams/1 unit (Carb Ratio)
Correction Factor (Insulin Sensitivity Factor)	Calculated based on Long Acting Dose	30 mg/dL/1 unit (Correction Factor)
Corresponding Control-IQ Settings		
Total Daily Insulin (required to enable Control-IQ)	Calculated based on Long Acting Dose	58 units/day (Total Daily Insulin)

Additional Pump Initiation Settings	
Insulin Duration Available range: 2 to 8 hours (default is 5 hours)	Insulin Duration for t:slim Pump: 5
Bolus Calculator Target BG (ADA Recommendations*) Adolescent and Young Adult (13-19 years old) Premeal: 90-130 mg/dL Bedtime/Overnight: 90-150 mg/dL Adult (>19 years old) Premeal: 70-130 mg/dL Bedtime/Overnight: <180 mg/dL	Target BG for t:slim Pump: 110 (Single number target)

161  
162

**Figure 1.** Insulin pump initiation settings worksheet

163 Adaptation will be recommended by the automated system, emailing written recommendations  
164 for settings changes to physicians for their review. The automated settings adaptation system will  
165 recommend a single basal rate, carbohydrate ratio and correction factor throughout the day  
166 (Figure 2), and will limit recommendations to a maximum 5% change at a time.

Report for serial number 660396 generated at 2021-07-14 08:02

Data was analyzed from 2021-06-12 08:00:00 to 2021-06-18 15:54:45 (last upload date)

Recommendations are based on the most frequently used profile (Main)

	Current	Recommended
BR	2.500	2.500
CR	4.0	4.0
ISF	19	19

There were no settings changes during this period

The profile 'Main' used the following segment(s):

Time	BR	CR	ISF
12:00 AM	2.5	4.0	19

Recommended settings aim to limit the amount of time below a specific glucose level if no changes to settings are made

Estimated probability of going below 70 mg/dL during basal: 0.46%

Estimated probability of going below 110 mg/dL during basal: 6.15%

Estimated probability of going below 70 mg/dL postprandially: 0.50%

Estimated probability of going below 110 mg/dL postprandially: 10.22%

Number of times we estimate hypoglycemic treatments were given in response to predicted lows during basal: 0

Number of times we estimate hypoglycemic treatments were given in response to predicted lows postprandially: 1

167

168 **Figure 2.** Sample E-Mailed Adaptation Settings Recommendations

169 If the user or study staff has manually changed settings to more than one timepoint per day, the  
170 settings adaptation system will continue to adapt back to one setting per day for basal rate,  
171 carbohydrate ratio and correction factor as shown in Figure 3.

---

Confidential

Contains trade secrets and/or confidential information exempt from disclosure from 21 CFR 20.61

Report for serial number 91634002 generated at 2021-07-14 07:59

Data was analyzed from 2020-08-29 12:59:19 to 2020-09-04 23:59:43. There was no upload during this period

Recommendations are based on the most frequently used profile (Weekday)

	Current	Recommended
BR	0.250	0.237
CR	30	28
ISF	135	128

Settings were changed at the following time(s):

Profile Name	
Weekday	2020-08-29 12:55:00
Weekday	2020-08-29 12:55:38
Weekday	2020-08-29 12:56:13
Weekday	2020-08-29 12:56:43
Weekday	2020-08-29 12:57:14
Weekday	2020-08-29 12:58:15
Weekday	2020-08-29 12:59:00
Weekday	2020-08-29 12:59:19
Weekend	2020-08-29 13:05:09
Weekend	2020-08-29 13:07:57
Weekend	2020-08-29 13:10:06
Weekend	2020-08-29 13:10:46
Weekend	2020-08-29 13:13:41
Weekend	2020-08-29 13:14:17
Weekend	2020-08-29 13:14:43
Weekend	2020-08-29 13:14:59

The profile 'Weekday' used the following segment(s):

Time	BR	CR	ISF
12:00 AM	0.38	30.0	135
02:00 AM	0.25	12.0	130
06:00 AM	0.28	10.0	120
08:00 AM	0.28	13.0	120
12:00 PM	0.34	20.0	95
02:00 PM	0.44	13.0	90
06:00 PM	0.44	18.0	85
09:00 PM	0.4	18.0	85

172

173 **Figure 3.** Sample E-Mailed Adaptation Settings Recommendations where more than one time point was entered, and the system has changed back to one time point to continue adaptation.

174 The report notes all the dates and times settings were changed since the last report.

175  
176 Physician overrides of the system, or changes to pump settings between emailed  
177 recommendations, will be documented with the reason for the override/settings change on the  
178 study case report form.

179

Confidential

Contains trade secrets and/or confidential information exempt from disclosure from 21 CFR 20.61

180 **5 STUDY OBJECTIVES, DESIGNS AND ENDPOINTS**

181 **5.1 STUDY OBJECTIVES**

182 **Primary objective:** To demonstrate the safety of the settings initialization and adaptation  
183 algorithm when in conjunction with Control-IQ technology, by assessing the number of severe  
184 hypoglycemic events (needing assistance) compared to expected incidence

185 **Secondary objective:** Compare time in range metrics and adverse events in the full 24 hour period,  
186 overnight and during the day, after each week of settings adaptation. The number of physician  
187 overrides/physician initiated changes in pump settings will also be tracked.

188 **5.2 STUDY DESIGN**

189 This feasibility study is a prospective, single arm study, evaluating an algorithm to recommend  
190 insulin pump settings at pump start (initialization) and then adjust settings at 3 days, at 7 days,  
191 and then weekly through 13 weeks.

192 Adults (age  $\geq$  18 years of age) with type 1 diabetes, who are using multiple daily injections, will  
193 be required to collect baseline CGM data for the first 2 weeks if not already Dexcom G6 users  
194 with at least 11 of 14 days of CGM use for the 14 days prior to enrollment. They may repeat this  
195 14 day run-in period if adequate CGM data is not collected, or study staff feel it is necessary to  
196 continue to monitor their insulin dose.

197 Up to 45 subjects may sign the consent form and be screened, with the goal that up to 30 subjects  
198 start use of the study device, and at least 20 subjects complete the trial.

199 Enrollment goals for baseline A1c at screening are:

200     • At least 5 subjects with A1c 8% - 8.9%  
201     • At least 5 subjects with A1c  $\geq$  9%

202 Subjects will then proceed to pump/Control-IQ training, where an algorithm based worksheet  
203 will be used to recommend initial basal rate, carbohydrate ratio and correction factor settings.

205 Subjects will then wear the insulin pump with Control-IQ technology active, and at 3 days after  
206 training, 7 days after training, and then every 7 days will:

207     1) Upload their pump using the USB uploader  
208     2) Have their study physician review the settings recommendations on the pump download  
209        report that will appear after each download.  
210     3) Change their settings after being called by the study physician to match the new  
211        recommendations.  
212     4) Upload their pump again so the study physician can verify the settings have been changed  
213        appropriately, and the correct settings changes were implemented on the correctly  
214        assigned pump by looking at the pump serial number on the settings report.

215 Physicians can at any time adjust pump settings and override the settings adaptation  
216 recommendations for safety concerns, and convert scheduled phone follow-up visits to in clinic  
217 visit at their discretion.

218 After 13 weeks (3 months) of use, subjects will return to clinic for a final visit.

219 Subjects who agree to provide their contact information will be offered an open ended interview  
220 at the end of the study to discuss their confidence in the automated settings recommendations  
221 and how it worked for them.

222 The data collected in this study will be directly entered into the eCRF (as applicable) or paper  
223 source forms. Subject data will include demographics, focused medical history, therapy data, and  
224 baseline and follow-up measures. All device data will be collected digitally and downloaded  
225 directly into the manufacturer provided software for the study devices.

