	
 
m. Adverse Device Effects
 
n. Serious Adverse Events
 
o. Change in total daily insulin use, basal and bolus
 
p. Number of physician overrides/physician initiated changes in pump settings
 
q. Patient Reported Outcomes
 

Duration of Study	Up to 17 weeks total, to allow for 2 to 4 weeks of CGM run-in if needed, then 13 weeks of pump/AID use with weekly settings adaptation
Study Design	
Adults (age <math>\geq</math> 18 years of age) with type 1 diabetes, who are using multiple daily injections, will be required to collect baseline CGM data for the first 2 weeks if not already Dexcom G6 users with at least 11 of 14 days of CGM use for the 14 days prior to enrollment. They may repeat this 14 day run-in period if adequate CGM data is not collected, or study staff feel it is necessary to continue to monitor their insulin dose.
 
Subjects will then proceed to pump/Control-IQ training, where an algorithm performed on a paper worksheet will be used to recommend initial basal rate, carbohydrate ratio and correction factor settings.
 
Subjects will then wear the insulin pump with Control-IQ technology active for 13 weeks, and at day 3 and at the end of each week will:
 
 
1) Upload their pump using the USB uploader
 
2) Have their study physician review the settings recommendations on the pump download report that will appear after each download.
 
3) Change their settings after being called by the study physician to match the new recommendations.
 
4) Upload their pump again so the study physician can verify the settings have been changed appropriately, and verify the correct settings have been applied to the correct pump assigned to the subject by verifying the serial number on the recommendations report to the changes in t:connect.
 
5) Physicians can at any time adjust pump settings and override the settings adaptation recommendations for safety concerns, and convert scheduled phone follow-up visits to in clinic visit at their discretion.
 
 
A semi-structured one-on-one interview may be completed concurrent with the 13-Week Visit or within a 28-day period following that visit. The interview will last approximately 30 minutes and will be conducted by Tandem staff using a script of open-ended questions to gather feedback and reactions to the

---

Confidential

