355 At each visit, the study pump and CGM data will be downloaded, and insulin delivery settings as  
356 recommend by the algorithm will be emailed to study staff for provider review. Providers will  
357 call the subjects for their scheduled appointment, and have the subjects enter the new pump  
358 settings, and then re-upload their pump to confirm the changes were implemented correctly,  
359 verifying the settings were applied to the correct pump serial number as assigned to that subject.

360 At any time, study staff providers may override the algorithm settings recommendations, either  
361 at or in between scheduled visits for safety concerns. The reason for any changes to override  
362 pump settings will be documented.

363 Unscheduled visits may occur at any time, and may be initiated by study staff or by study  
364 subjects.

365 A semi-structured one-on-one interview may be completed concurrent with the 13-Week Visit or  
366 within a 28-day period following that visit. The interview will last approximately 30 minutes and  
367 will be conducted by Tandem staff using a script of open-ended questions to gather feedback and  
368 reactions to the automated initialization and adaptation system, as well as the use of Closed-Loop  
369 Control.

370 Interview sessions may be audio- or video-taped and transcribed by a professional transcription  
371 service. Otherwise, these recordings will not be shared for any non-study purposes.  
372 Transcriptions will use a code for participants, such as "Participant 1", and will not contain  
373 names or other identifiers of participants.

374 **Observation and Recording of Adverse Events:** Subjects will be required to report AEs. Open-  
375 ended questions and questions specific to SH and DKA will be included in all subject visits. An  
376 AE form will be completed for every adverse event reported by a subject. Any medical  
377 management of an event and the resolution of the event must be recorded in source  
378 documentation and on the appropriate eCRF using medical terminology.

379 **Treatment of hyper- and hypoglycemia:** Procedures in Section 10.9 and 10.10 will be  
380 followed by study staff and by subjects.

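### For a profile with several time segments, the 5% limit in Section 4.3 is measured from an undefined reference value, so the change actually entered can be far larger than the report shows

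*Combined protocol and SAP*

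**What the plan says.** Section 4.3 makes two statements about the algorithm's output. It will "recommend a single basal rate, carbohydrate ratio and correction factor throughout the day", "and will limit recommendations to a maximum 5% change at a time". The base for the 5% is not stated.

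The same section covers profiles that a user or staff member has split by time of day: the "settings adaptation system will continue to adapt back to one setting per day for basal rate", and likewise for the other two settings, with Figure 3 cited as the example. The Figure 3 caption describes a report "where more than one time point was entered, and the system has changed back to one time point to continue adaptation". Its basal line reads "BR 0.250 0.237" (current, then recommended), although the profile printed below has eight segments. The report says that it works from the most frequently used profile. It does not say how one value per setting is drawn from that profile.

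On use of the report, the Synopsis has subjects "Change their settings after being called by the study physician to match the new recommendations". Section 7.4 adds the safeguard: "At any time, study staff providers may override the algorithm settings recommendations, either" at scheduled visits or between them, for safety concerns and with the reason documented.

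**The concern.** The 5% limit is the only stated bound on how far one algorithm recommendation can move a setting, in a study whose primary objective is that algorithm's safety. A physician who relies on Section 4.3 would take each step to be small. For a segmented profile the step may be small only against a reference value that the subject is not using.

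Direction can mislead as well as size. In Figure 3 the carbohydrate ratio appears to go from 30 to 28, a slight move towards more meal insulin. Entering 28 all day gives less meal insulin in seven of the eight segments (22 of 24 hours).

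The situation can also follow a safety adjustment. If staff segment a profile in response to a problem, as Sections 7.4 and 7.6 allow, the next report will propose to remove the segments.

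**Working it through.** **Inputs (all from Figure 3).** Current to recommended: basal rate (BR) 0.250 to 0.237 U/h, carbohydrate ratio (CR) 30 to 28 g/U, correction factor (ISF) 135 to 128 mg/dL per U. The segments are in the table below.

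**1. Reproduce the 5%.** Take 0.95 times the 'Current' column:

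- BR: 0.95 × 0.250 = 0.2375
- CR: 0.95 × 30 = 28.5
- ISF: 0.95 × 135 = 128.25

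Cutting off the extra digits gives 0.237, 28 and 128, exactly the recommended column. So the limit is applied to that column. The printed changes are then 5.2%, 6.7% and 5.2%, each slightly over 5% because of truncation.

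**2. Identify the base.** 0.250 is the lowest of the eight basal rates (2 AM). 30 and 135 are the highest CR and ISF (midnight). No segment holds all three, so the 'Current' set is in force at no hour.

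**3. Compare with the settings in force.** For fixed carbohydrate, meal insulin is proportional to 1/CR, so its change is old CR/28 − 1. Correction insulin changes by old ISF/128 − 1. Basal changes by 0.237/BR − 1.

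| Start | Hours | BR | CR | ISF | Basal | Meal insulin | Correction insulin |
|---|---|---|---|---|---|---|---|
| 12 AM | 2 | 0.38 | 30 | 135 | −37.6% | +7.1% | +5.5% |
| 2 AM | 4 | 0.25 | 12 | 130 | −5.2% | −57.1% | +1.6% |
| 6 AM | 2 | 0.28 | 10 | 120 | −15.4% | −64.3% | −6.2% |
| 8 AM | 4 | 0.28 | 13 | 120 | −15.4% | −53.6% | −6.2% |
| 12 PM | 2 | 0.34 | 20 | 95 | −30.3% | −28.6% | −25.8% |
| 2 PM | 4 | 0.44 | 13 | 90 | −46.1% | −53.6% | −29.7% |
| 6 PM | 3 | 0.44 | 18 | 85 | −46.1% | −35.7% | −33.6% |
| 9 PM | 3 | 0.40 | 18 | 85 | −40.8% | −35.7% | −33.6% |

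**4. Daily basal.** Sum of BR × hours = 0.76 + 1.00 + 0.56 + 1.12 + 0.68 + 1.76 + 1.32 + 1.20 = 8.40 U. After entry: 24 × 0.237 = 5.688 U, and 5.688/8.40 − 1 = −32.3%. Most of this comes from collapsing the segments: 24 × 0.250 = 6.00 U is already 28.6% below 8.40 U. The algorithm's own step takes 6.00 to 5.688 U (−5.2%).

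**5. One meal.** For 60 g at 7 AM, 60/10 = 6.0 U before and 60/28 = 2.1 U after.

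**6. When could one value stay within 5% of every segment?** It must lie between 0.95 × max and 1.05 × min, so max/min can be at most 1.05/0.95 = 1.105. In Figure 3 the ratios are 0.44/0.25 = 1.76, 30/10 = 3.00 and 135/85 = 1.59. This bound matters only if the limit is meant to hold in each segment, which the text does not say.

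**The case against.** The strongest reply is that Section 4.3 never promises 5% in every segment. Against the report's own 'Current' column the limit holds apart from truncation, as step 1 shows. A reader might infer that the plan contradicts itself and that no single value can keep the limit once segments differ by more than 10.5%. That follows only under a per-segment reading which the text does not state. What remains is that the base is undefined and, in the plan's own example, does not describe the profile in use.

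Second, Figure 3 is a sample report with 2020 data and separate weekday and weekend profiles. Trial subjects come from injections, and the Figure 1 worksheet starts them on one profile with one segment. Nothing suggests that staff would create a CR range of 10 to 30. This stands: 32% and 64% describe the example and do not forecast what participants will experience.

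Third, there are safeguards. The report prints every segment and every change time, the physician reviews it before calling the subject, and overrides are allowed. Control-IQ modulates basal delivery and gives automated corrections, so delivered insulin would change by less than programmed insulin. A reader might infer that under-delivery would go unseen because the primary endpoint counts severe hypoglycemia. However, Section 5.3 includes DKA, time above 180 and 250 mg/dL, and weekly CGM comparisons. Section 10.9 gives a hyperglycemia and ketone protocol, Section 11.4 makes ketosis events reportable, and Section 11.13 has a criterion of three or more severe hyperglycemia cases. These lower the risk, but they do not correct a report that shows no percent change per segment or in total daily basal.

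Finally, the wording on adapting back could mean a gradual return. The Figure 3 caption and the single recommended value per setting show the collapse in one report, and no stepwise rule is given.

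**Conclusion.** The concern holds as a minor defect limited to segmented profiles. There, the stated maximum of 5% does not bound the change the subject would enter, because the reference value is undefined and all segments are replaced at once. In the plan's example, reported changes of 5.2% to 6.7% correspond to −32% in programmed daily basal and −64% in 6-8 AM meal insulin.

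These sizes assume a full day on the printed weekday profile, equal carbohydrate before and after, and programmed rather than delivered insulin. The 64% covers the meal component only. How often the case will arise cannot be derived from the documents. Single-segment profiles, the starting state, are affected only by rounding.

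In the example nearly all the change is towards less insulin. A reader might infer the opposite hazard: a single value near the average would reverse an overnight reduction made for lows. The documents give no support for averaging; the only example uses the least-insulin value for all three settings.

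**What to change.** In Section 4.3, state that the 5% limit is measured against the settings in force, and add:

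*If the profile has more than one segment and entering the single recommended value would change any segment by more than 5% (apart from pump rounding), the recommendation is not entered. The study physician sets the profile, after reviewing the percent change per segment and in total daily basal, and records it as an override.*

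This needs no software change: the report already lists the segments, so staff can work out the percentages, and override reasons already go on the case report form. The cost is some added overrides in endpoint p and a slower return to one setting. By step 6, any profile whose segments differ by a ratio above 1.105 would take this route.

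Two other remedies are not recommended. Rounding towards the current value would freeze whole-number settings below 20: 10 × 1.05 = 10.5 goes back to 10, and the Figure 2 correction factor of 19 gives 19 × 0.95 = 18.05, which goes back to 19. Automatic stepping of each segment would test a different algorithm from the one-setting-per-day product under study.

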### 226 **5.3 STUDY ENDPOINTS**

227 1) Primary Endpoint:

- 228 a. To demonstrate the safety of the system, by assessing the number of severe  
229 hypoglycemic events (needing assistance) compared to expected incidence

230 2) Secondary Endpoints:

- 231 a. Time in range 70-180 mg/dL
- 232 b. Time < 54 mg/dL
- 233 c. Time < 70 mg/dL
- 234 d. Time > 180 mg/dL
- 235 e. Time > 250 mg/dL
- 236 f. Time in tight glycemic range 70-140 mg/dL
- 237 g. Post-prandial glycemic peak
- 238 h. 4-hour post meal glucose AUC
- 239 i. Sensor glucose median and interquartile range
- 240 j. CGM metrics daytime vs. nighttime
- 241 k. CGM metrics compared each week after adaptation
- 242 l. DKA
- 243 m. Serious Adverse Events
- 244 n. Adverse Device Effects
- 245 o. Change in total daily insulin use, basal and bolus
- 246 p. Number of physician overrides/physician initiated changes in pump settings
- 247 q. Patient Reported Outcomes

248 **6 SUBJECT SELECTION**

249 **6.1 SUBJECT POPULATION**

250 **6.1.1 INCLUSION CRITERIA:**

251 Eligibility to enroll in the study will be assessed based on the following inclusion criteria:

- 252 1) Adult subjects  $\geq$  age 18 years
- 253 2) Clinical diagnosis of type 1 diabetes for at least one year
- 254 3) Using a basal/bolus regimen by injection (MDI therapy)
- 255 4) Total daily dose  $\geq$  10 units/day
- 256 5) Willing to use only aspart (novolog) or lispro (humalog) U-100 insulin with the study  
257 pump.
- 258 6) A1c  $\geq$  7.5% and  $\leq$  11% at screening
- 259 7) Not pregnant or planning a pregnancy during the time period of the study.
- 260 8) Has current glucagon product to treat severe hypoglycemia (injectable or nasal) at home  
261 (will provide prescription if they do not have one)
- 262 9) Willingness to follow study procedures and a signed informed consent form

263 **6.1.2 EXCLUSION CRITERIA:**

264 Eligibility to enroll in the study will be assessed based on the following exclusion criteria:

- 265 1) Two or more episodes of severe hypoglycemia (needing assistance) in the past 6 months
- 266 2) Two or more episodes of diabetic ketoacidosis in the past 6 months
- 267 3) Inpatient psychiatric treatment in the past 6 months
- 268 4) History of drug abuse (defined as any illicit drug use) or history of alcohol abuse prior to  
269 screening or unwillingness to agree to abstain from illicit drugs throughout the study
- 270 5) Significant chronic kidney disease or hemodialysis
- 271 6) Significant liver disease
- 272 7) History of adrenal insufficiency
- 273 8) Hypothyroidism or hyperthyroidism that is not appropriately treated
- 274 9) Other chronic disease/condition determined by investigator to interfere with participation  
275 in the study
- 276 10) Use of glucocorticoids, beta blockers or other medications determined by investigator to  
277 interfere with study
- 278 11) Use of long-acting insulin, inhaled insulin (Afrezza), or use of any non-insulin glucose  
279 lowering agents (i.e. SGLT-2 inhibitor) other than Metformin with the study pump
- 280 12) Subject is pregnant or lactating or intending to become pregnant before or during  
281 participation in this study.
- 282 13) Investigator judgement that subject would not be able to complete the trial.

283 **6.2 SUBJECT WITHDRAWAL OR TERMINATION**

284 Subjects are free to withdraw from the study at any time and will be withdrawn if they inform the  
285 study team that they no longer wish to participate. Data collected prior to the subject's  
286 withdrawal will remain part of the study record and will be included in the analyses.

287

288

---

Confidential

*Contains trade secrets and/or confidential information exempt from disclosure from 21 CFR 20.61*

289 **7 TREATMENT OF SUBJECTS**

290 **7.1 THE T:SLIM X2 INSULIN PUMP WITH CONTROL-IQ**  
291 **TECHNOLOGY**

292 The Control-IQ System is a US FDA approved device indicated for the treatment of type 1  
293 diabetes in people age 6 years and older. The Control-IQ System is integrated with the Dexcom  
294 G6 CGM and uses CGM values to adjust insulin delivery with the goal of improving glucose  
295 control (time in range of 70-180 mg/dL).

296 For the current study, subjects will use t:slim X2 pump with Control-IQ technology cleared  
297 under K201214 and K200467, respectively.

298 **7.2 ENROLLMENT PROCEDURE:**

299 Potential study subjects will be recruited by the clinical site. After a description of the study is  
300 provided by the study team, the subject will be asked to sign the informed consent form (ICF).  
301 Eligibility to enroll in the study will be assessed based on the inclusion/exclusion criteria.  
302 Enrollment information will be entered onto the study case report forms. In addition,  
303 demographic and relevant medical history will be collected at this time and entered onto the  
304 study case report forms.

305 **7.3 DURATION OF THERAPY AND FOLLOW-UP:**

306 Each enrolled subject may participate for ~17 weeks total, to allow for 2 to 4 weeks of CGM  
307 run-in if needed, then 13 weeks of pump/AID use with weekly settings adaptation.

308 **7.4 STUDY PROCEDURES:**

309 **Event Schedule:** The CRFs will be completed by the investigator (or an authorized member of  
310 the investigator's staff) per the event schedule described below.

311

312 **Table 1.** Schedule of Visits and Procedures

	Screening Visit	CGM Run-in Visit (may be repeated after 2 weeks)	Pump and Control-IQ Training Visit	Control-IQ Use					
		2-4 weeks		3d	7d	Weekly	13w	F/U Call	UV
Visit (V) or Contact (C)	V	V	V	C	C	C	V	C	C/V
Informed Consent	X								
Eligibility Assessment	X								
Medical history/physical exam	X								
Vital Signs	X								
HbA1c (POC or local lab for inclusion criteria confirmation)	X								
HbA1c (Central lab)			X				X		
Pregnancy test (females of child-bearing potential)	X		X						
Assessment of CGM use	X	X							
Study system training		X	X						
AE Assessment		X	X	X	X	X	X	X	X
Upload device data from home				X	X	X			X
Download device data at clinic visit	X	X	X				X		X
Open Ended Interview							X		

313

314 **Baseline Data Collection:** Adults (age  $\geq$  18 years of age) with type 1 diabetes, who are using multiple daily injections, will be required to collect baseline CGM data for the first 2 weeks if not already Dexcom G6 users with at least 11 of 14 days of CGM use for the 14 days prior to enrollment. They may repeat this 14 day run-in period if adequate CGM data is not collected.

318 **Subject Completion or Early Withdrawal:** The subject completes the study approximately 17-21 weeks after enrollment, or when they choose to withdraw from the study, if earlier than the final visit

321 **Data Collection:** Investigators will assign a de-identified number to each subject and will be required to keep any study paperwork or electronic files in a secure private area. Monitoring will be conducted to help ensure that data is secure and entered within reasonable limits, consistent with a risk-based monitoring approach.

325 **Demographics:** The following demographic data will be obtained: date of birth, gender, race,  
326 ethnicity, educational level, socioeconomic status, residence, employment status, weight, height,  
327 blood pressure, pulse, and type of health insurance.

328 **Medical History:** Medical history, including existing comorbidities deemed clinically relevant  
329 (e.g. retinopathy, nephropathy, neuropathy, history of cardiovascular events) will be collected at  
330 baseline. In addition, details specific to type 1 diabetes, including age at diagnosis, duration of  
331 disease, and previous therapy will be collected from the study subject and documented in the  
332 subject's eCRF. A new hemoglobin A1c will also be obtained at the screening visit, at  
333 randomization and at end of study.

334 **Pregnancy:** In order to reduce the risk of pregnancy, subjects of childbearing potential must  
335 agree to use an effective method of birth control while participating in this study. Acceptable  
336 methods of birth control for use in this study are barrier methods, intrauterine devices, or oral  
337 contraceptive pills. The Investigator or study staff will discuss this with the subject.

338 **Device Training:** All subjects will complete study device training before starting use of the  
339 study device. Subjects will be trained by qualified study staff using the study approved device  
340 training checklists, and will be given a copy of the Study Participant Instruction Sheet. In  
341 addition to device training, the Study Participant Instruction Sheet reviews procedures for  
342 checking ketones, and when to contact study staff for assistance.

343 All subjects will complete CGM training. Subjects who are not already Dexcom G6 users with at  
344 least 11 of 14 days of CGM use for the 14 days prior to enrollment will complete CGM run-in.  
345 They may repeat this 14 day run-in period if adequate CGM data is not collected.

346 All subjects will complete insulin pump training. The pump training visit may be extended over  
347 more than one day if needed in the judgement of the investigator. Initial pump settings will be  
348 configured by following the study settings algorithm worksheet. At the end of the pump training  
349 visit, subjects will activate Control-IQ technology

350 Subjects will wear the insulin pump with Control-IQ technology active in the outpatient setting,  
351 and have scheduled phone follow up visits at 3 days (+/- 1 day), 7 days (+/- 2 days), then weekly  
352 (+/- 3 days). A final visit in clinic will occur at 13 weeks (+/- 7 days). A post final clinic visit  
353 phone call will occur 3 days (+/- 1 day) after changing back to MDI therapy after the study  
354 devices are returned.

355 At each visit, the study pump and CGM data will be downloaded, and insulin delivery settings as  
356 recommend by the algorithm will be emailed to study staff for provider review. Providers will  
357 call the subjects for their scheduled appointment, and have the subjects enter the new pump  
358 settings, and then re-upload their pump to confirm the changes were implemented correctly,  
359 verifying the settings were applied to the correct pump serial number as assigned to that subject.

360 At any time, study staff providers may override the algorithm settings recommendations, either  
361 at or in between scheduled visits for safety concerns. The reason for any changes to override  
362 pump settings will be documented.

363 Unscheduled visits may occur at any time, and may be initiated by study staff or by study  
364 subjects.

365 A semi-structured one-on-one interview may be completed concurrent with the 13-Week Visit or  
366 within a 28-day period following that visit. The interview will last approximately 30 minutes and  
367 will be conducted by Tandem staff using a script of open-ended questions to gather feedback and  
368 reactions to the automated initialization and adaptation system, as well as the use of Closed-Loop  
369 Control.

370 Interview sessions may be audio- or video-taped and transcribed by a professional transcription  
371 service. Otherwise, these recordings will not be shared for any non-study purposes.  
372 Transcriptions will use a code for participants, such as "Participant 1", and will not contain  
373 names or other identifiers of participants.

374 **Observation and Recording of Adverse Events:** Subjects will be required to report AEs. Open-  
375 ended questions and questions specific to SH and DKA will be included in all subject visits. An  
376 AE form will be completed for every adverse event reported by a subject. Any medical  
377 management of an event and the resolution of the event must be recorded in source  
378 documentation and on the appropriate eCRF using medical terminology.

379 **Treatment of hyper- and hypoglycemia:** Procedures in Section 10.9 and 10.10 will be  
380 followed by study staff and by subjects.

